#### Medical device classification

The APDC is a Class III Medical Device in accordance with the UK Medical Devices Regulations 2002, SI 618 (UK MDR 2002). The APDC is defined as a medical device in accordance with Part I, Regulation 2 of the UK MDR 2002 which includes in its definition of a medical device "....devices intended to administer a medicinal product or which incorporate as an integral part a substance which, if used separately, would be a medicinal product and which is liable to act upon the body with action ancillary to that of the device". The APDC is classified as a Class III medical device in agreement with UK MDR 2002 Part II, Regulation 7 which is in accordance with Rule 13 of Annex IX of Directive 93/42, which states "All devices incorporating, as an integral part, a substance which, if used separately, can be considered to be a medicinal product, as defined in Article 1 of Directive, and which is liable to act on the human body with action ancillary to that of the devices, are in Class III."

## Comparator

There is no comparator device in this study.

## 7.2. Traceability of the Device

The antimicrobial PD catheters will not be loaned or gifted to participants. They will be inserted by the direct care team at UHDB. Each catheter has a unique reference number that is recorded both in the patient record and in the CRF.

## 7.3. Investigator Brochure (IB)

An Investigator Brochure is available for the APDC.

All antimicrobial peritoneal dialysis catheters will come supplied with instructions for use (IFU) in each package.

## 7.4. Device Storage, Supply and Accountability

The APDC should be stored at controlled room temperature (protected from excessive heat) and protected from light and humidity. The devices will be stored in a locked cupboard at UHDB separate to any routine clinical supplies.

If a PD catheter is removed for any reason during the study period the PD catheter will be retained for further analysis by the study team. The PD catheter and its components will be destroyed by incineration after the laboratory analyses are completed.

There will be no post-trial access to the device.

## 7.5. Assessment of Compliance

This is an implanted device, the use and functioning of the device will be monitored at a minimum frequency of monthly once established on therapy and more frequently if there are any concerns.

## 8. PHARMACOVIGILANCE

## 8.1. Definitions

Term	Definition
Adverse Event (AE) Adverse Device	Any untoward medical occurrence, unintended disease or injury, or untoward clinical signs (including abnormal laboratory findings) in subjects, users or other persons, where or not related to the investigational medical device and whether anticipated or unanticipated.
Effect (ADE)	
 
An adverse event related to the use of an investigational medical device.
 
NOTE: this definition includes: 
 
AEs resulting from insufficient or inadequate instructions for use, deployment, implantation, installation, or operation, or any malfunction of the investigational medical device.
 
Any event resulting from use error or from intentional misuse of the
 

	
 
investigational medical device.
 
'Comparator' if the comparator is a medical device.
 

Serious Adverse Event (SAE)	
 
An adverse event that led to any of the following: 
 
death
 
serious deterioration in the health of the subject, users, or other persons as defined by one of more of the following 
 
a life-threatening illness or injury, or
 
a permanent impairment of a body structure or a body function including chronic diseases, or
 
in-patient of prolonged hospitalisation, or
 
medical or surgical intervention to prevent life-threatening illness or injury, or permanent impairment to a body structure of a body function,
 
 
 
foetal distress, foetal death, a congenital abnormality, or birth defect including physical or mental impairment.
 
 NOTE: Planned hospitalisation for a pre-existing condition, or a procedure required by the CIP without a serious deterioration in health, is not considered a SAE.

Serious Adverse	An adverse device effect that has resulted in any of the consequences
Device Effect (SADE)	characteristic of a serious adverse event.
Unanticipated Serious Adverse Device Effect (USADE)	A serious adverse device effect which by its nature, incidence, severity or outcome has not been identified in the current risk assessment. NOTE: Anticipated serious adverse device effect (ASADE) is an effect which by
	its nature, incidence, severity or outcome has been identified in the risk assessment.

Device Deficiency	
 
Inadequacy of a medical device with respect to its identity, quality, durability, reliability, usability, safety or performance.
 
NOTE: This definition includes: 
 
Malfunctions, use errors, and inadequacy in the information supplies by the manufacturer including labelling.
 
Device deficiencies related to the investigational medical device or the comparator.
 
 
 

Serious Health Threat	Signal from any adverse event or device deficiency that indicates an imminent risk of death or a serious deterioration in the health in subjects, users or other persons, and that requires prompt remedial action for other subjects, users or other persons. NOTE: this would include events that are of significant and unexpected nature such that they become alarming as a potential serious health hazard or possibility of multiple deaths occurring at short intervals.

## 8.2. Operational Definitions for (S)AEs

(S)AEs that require reporting to the Sponsor will include;

Any episode of hospital admission or attendance related to a suspected reaction to the PD catheter Any episode of infection where resistance to any of the antibiotics used in this catheter is identified. Any incidence of the catheter migration/falling out.

The following events will not be considered (s)AE's;

Treatment which was elective or pre-planned, for a pre-existing condition not associated with any deterioration in condition.

Any admission to hospital or other institution for general care where there was no deterioration in condition.

Routine treatment or monitoring of the studied indication not associated with any deterioration in condition.

Treatment on an emergency, outpatient basis for an event not fulfilling any of the definitions of serious as given above and not resulting in hospital admission.

Foreseeable adverse events and the management of these are described in section 7.7 Trial assessments and associated appendices and do not need to be reported to the sponsor but will be recorded in the participants medical records. Episodes of PD related peritonitis infection occur at a rate of around 0.37 infections per patient year in our current population. A rate of peritonitis above this in our study population will require review at the trial management committee.

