4. PD prescription details will be recorded and the reason for any change in prescription will be logged.

All blood and PD fluid tests will be part of routine care. All study visits will coincide with routine clinical visits. The IPOS Renal questionnaire is in addition to routine care. At 24 weeks after PD catheter insertion the study will be considered completed and individuals will continue with routine clinical care. Additional visits will be arranged if there are any concerns raised between routine visits.

Additional visits for foreseeable adverse events related to treatment with a PD catheter : See Figure 2, Figure 3, and Figure 4 for the flow diagrams of participant care leading to additional study visits

Any episode of PD related infection (exit site, tunnel or Peritonitis) will result in an extra visit and investigation/ treatment as per existing guidelines (Appendix 4 - PD Peritonitis Guideline). The results of these investigations and the clinical outcome will be recorded. If any microorganisms are isolated during the routine clinical processing of samples this isolate will be stored.

If a PD catheter is removed for any reason during the study period the catheter will be retained for further analysis by the study team.

All adverse events reported by participants will be recorded. Individuals transferring off PD will be recorded but individuals who stop PD due to a functioning kidney transplant or recovery of independent kidney function will not be recorded as adverse events.

In the event that a participant moves away for the area the receiving team will be informed of the fact that they are participating in a study and no further data will be collected. Due to the nature of the treatment and the relatively short duration of the study it is very unlikely that participants will otherwise be "lost to follow up" but every effort will be made to contact them and ensure appropriate follow up.

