## 8.3. Recording and Reporting SAEs and USADEs

All AEs, SAEs and device deficiencies must be recorded from the time of written informed consent until 26 weeks after the insertion date.

All AEs and device deficiencies occurring during the duration of the study must be reported by the investigator within the CRF. The PI is responsible for checking for AEs and SADEs when participants attend for treatment and follow-up.

The following events are considered reportable:

- Any SAE (whether initially considered device related or not)
- Any device deficiency that might have led to a SAE if:
  - o Suitable action had not been taken or
  - o Intervention had not been made or
  - If circumstances had been less fortunate.
- New findings/updates in relation to already reported events

All reportable events must be recorded by the investigator using the Sponsor's SAE reporting form and emailed to UHDB within 3 calendar days of the research team becoming aware of the event; even if not all information is available at the time (further information should be provided on the Sponsor's SAE Follow Up Report Form). Any change of condition or other follow-up information should be sent to the Sponsor as soon as it is available, or at least within 3 working days of the information becoming available. Events will be followed up until the event has been resolved or a final outcome has been reached. Safety information will be reviewed during trial management group meetings.

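### Section 8.2, read literally, denies adverse-event status to non-serious events treated as emergency outpatients, so the numerator of the primary rate depends on which section staff follow

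*Protocol*

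**What the plan says.** Section 8.2 gives operational definitions for (S)AEs. It opens with events that must be reported to the Sponsor, among them "Any episode of hospital admission or attendance related to a suspected reaction to the PD catheter". A second list follows under the lead-in "The following events will not be considered (s)AE's". Its first three items (elective or pre-planned treatment, admission for general care, routine treatment or monitoring) all require that the participant's condition has not deteriorated. The fourth has no such limit: "Treatment on an emergency, outpatient basis for an event not fulfilling any of the definitions of serious as given above", where no admission follows.

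Other sections are broader:

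- Section 8.1 defines an AE as "Any untoward medical occurrence, unintended disease or injury, or untoward clinical signs (including abnormal laboratory findings) in subjects, users or other persons", whether or not related to the device.
- Section 6.4 says "All adverse events reported by participants will be recorded".
- Section 8.3 says "All AEs, SAEs and device deficiencies must be recorded from the time of written informed consent until 26 weeks after the insertion date", and adds "All AEs and device deficiencies occurring during the duration of the study must be reported by the investigator within the CRF".

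The primary endpoint (2.3) is the rate of AEs attributable to the antimicrobials or the impregnation process. The primary analysis (10.3.2) reports counts by AE category and a rate per participant observation month. Neither sets a seriousness threshold.

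**The concern.** Emergency treatment is by nature unplanned and usually signals something new and untoward. A painful exit site, a leak or a rash that is treated the same day and sent home would meet the 8.1 definition, yet the fourth item of 8.2 says it is not an (s)AE. The wording suits a list of things that are not *serious* AEs, but the lead-in's abbreviation reaches non-serious AEs too.

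This bears on the primary outcome. Section 8.3.1.2 asks for a causality judgement on each AE. An event that is not treated as an AE never reaches that judgement and so cannot enter the attributable rate. The study has one arm and no comparator device (7.1, 10.5), so no control rate would show that events had been lost. Any loss runs in one direction, towards the conclusion that the catheter is well tolerated.

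**Working it through.** **Comparison of the passages.** Take a non-serious event, treated urgently at hospital as an outpatient, with no admission.

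| Section | What it says about this event |
|---|---|
| 8.1 | An AE; no condition on seriousness or place of care |
| 6.4 | Recorded, if the participant reports it |
| 8.3 | Recorded from consent to 26 weeks after insertion, and entered in the CRF |
| 8.3.1.1 | Gradable; the scale starts at mild and separates severe from serious |
| 8.2, first list | Reportable to the Sponsor, if the attendance relates to a suspected reaction to the catheter |
| 8.2, second list | Not an (s)AE |

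The last row conflicts with all the others. Within 8.2, a suspected catheter reaction treated at hospital and sent home falls under both lists.

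**Effect on the primary rate.** Inputs from Section 10.1: 40 participants, 6 months each.

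- Planned denominator: 40 × 6 = 240 patient months, which reproduces the protocol's figure. In years, 240 / 12 = 20.
- Rate per participant month = events / 240.
- Change for each event dropped: 1/240 = 0.0042 per participant month.
- Direction: the numerator falls and the denominator does not change, so the rate can only go down.

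For the attributable rate in 2.3, the same 0.0042 applies to each dropped event that would have been judged attributable. It is zero for the others.

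**Total effect.** This would be the number of dropped events × 0.0042. The protocol gives no expected number of non-serious events treated as emergency outpatients, so no total can be calculated.

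**The case against.** The strongest reply is that the list was only meant to say what is not an SAE, or what need not go to the Sponsor. Section 8.2 opens with reporting to the Sponsor, and its closing paragraph separates what need not be reported from what is still recorded. The disputed item itself turns on not being serious and not being admitted. On that reading no event is lost: 8.3 still puts every AE in the CRF, 6.4 still records what participants report, the assessment schedule in Appendix 1 has AE checks at visits 3 to 15 and at additional visits, and 10.3.2 carries no such exclusion. This reading is plausible, and it means that loss of events is a risk, not an established fact. It does not settle the matter, because the text does not say it. The section is headed as definitions, the lead-in speaks of what is considered an (s)AE and not of what is reported, and the first list includes events that need not be serious.

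A reader might infer two stronger claims that the protocol does not support.

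- *That a sizeable share of peritonitis would vanish.* At the local rate of 0.37 per patient year, 0.37 × 20 = 7.4 episodes would be expected. But the protocol does not say what share is managed without admission. Section 6.4 requires the results and outcome of every PD-related infection to be recorded, a separate sentence in 8.2 deals with foreseeable events, and peritonitis and exit-site/tunnel infection have their own secondary rates (2.4, 10.3.3). Nor is background peritonitis presumptively attributable to the antimicrobials.
- *That most hypersensitivity reactions would be lost.* The first list in 8.2 makes hospital attendance for a suspected catheter reaction reportable, which partly protects the events closest to the primary endpoint.

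**Conclusion.** The contradiction is real and concerns what counts in the primary numerator. Following 8.2 literally removes non-serious emergency-outpatient events; following 8.1, 6.4 and 8.3 keeps them. Most exposed are non-serious problems that are neither recognised as a suspected catheter reaction nor counted under an infection endpoint.

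The size is 0.0042 per participant month for each dropped event, always downward, assuming that all 40 participants contribute the full 6 months. With less follow-up the denominator is smaller and each event weighs more. The overall bias is unknown. The protocol does not show that events will be lost, only that it gives staff two incompatible rules. These should be reconciled before events are counted.

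**What to change.** Reword the lead-in to the second list in 8.2 so that it limits only SAE classification or reporting to the Sponsor, for example: the following will not be considered SAEs. Check the result against the first list, so that hospital attendance for a suspected catheter reaction is clearly still reportable.

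Add a sentence stating that every AE as defined in 8.1, from written informed consent to 26 weeks after insertion and however treated, is entered in the CRF, assessed for causality, and eligible for the primary outcome as defined in 2.3 and 10.3.2. The window should start at consent, to match 8.3. Eligible is the right word because 2.3 counts only attributable events.

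The cost is a small wording change, slightly more AE entry by research staff, and a reported AE rate that may be higher than under the literal 8.2 rule.

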#### **STUDY FLOW CHART**

[figure not shown]

Figure 1 Flow diagram of routine study visits, Items highlighted in red are additional to routine care.

[figure not shown]

Figure 2 Flow diagram of additional study procedures for PD peritonitis Items highlighted in Red are additional to routine care

[figure not shown]

Figure 3 Flow diagram for additional study procedures for exit site infections, Items highlighted in **Red** are additional to routine care

[figure not shown]

Figure 4 Flow diagram for additional study procedures if PD catheter to be removed as no longer required, Items highlighted in **Red** are additional to routine care

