The number of people performing PD in the UK is still small, with approximately 3500 prevalent PD patients and about 1700 incident patients annually (1). One of the biggest problems limiting PD use is PD catheter-related infection, classified by the site affected (exit site, catheter tunnel or peritonitis). Peritonitis can be severe, requiring hospital admission and urgent removal of the infected catheter. Infections are the major cause of hospital admissions, morbidity and mortality in PD patients and are the most common cause of PD catheter access failure within the first year (1). In 2016-17 the rate of PD related peritonitis averaged 40-50 episodes per 100 patient years across units in England and infections accounted for 20.3% of all deaths in people performing PD (1).

PD catheter infections are caused mainly by Staphylococcus aureus (including methicillin-resistant S. aureus), Staphylococcus epidermidis and Escherichia coli. A number of different approaches have been tried to reduce PD catheter infections with varying degrees of success (4). No anti-infective PD devices currently exist on the market. University of Nottingham (UoN) has developed and patented a method of impregnating, not coating, medical devices with antimicrobials to give extended protection from microbial colonisation (5). Pre-clinical studies show that PD catheters can be impregnated with the antimicrobials rifampicin, triclosan, and sparfloxacin to give long-term protection against the main causative agents of PD-associated infections. Bacteria accessing the catheter are killed and biofilm development is prevented (6).

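### Section 8.2 exempts foreseeable events, including peritonitis, from sponsor reporting without limiting this to non-serious events, while 8.3 makes every SAE reportable

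*Protocol*

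**What the plan says.** Section 8.2 of the protocol sets operational definitions for adverse events and SAEs together. It lists three kinds of event that go to the sponsor: hospital admission or attendance for a suspected reaction to the catheter, infection with resistance to one of the catheter's antibiotics, and catheter migration or loss. It then carves out foreseeable events. It locates them as follows: "Foreseeable adverse events and the management of these are described in section 7.7 Trial assessments and associated appendices". It adds that they "do not need to be reported to the sponsor but will be recorded in the participants medical records". The next sentence gives the local peritonitis rate of about 0.37 per patient-year and sends a higher study rate to the trial management committee.

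Section 8.3 lists as reportable "Any SAE (whether initially considered device related or not"), to be put on the sponsor's SAE form and "emailed to UHDB within 3 calendar days of the research team becoming aware of the event". It also requires: "All AEs and device deficiencies occurring during the duration of the study must be reported by the investigator within the CRF".

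Section 8.3.2, which covers devices that are not CE-marked or are used outside their marked purpose, sends all reportable events on to the regulator and the manufacturer.

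**The concern.** The two sections give opposite instructions for an event that is both foreseeable and serious. Peritonitis is the obvious case, because the Background says: "Peritonitis can be severe, requiring hospital admission and urgent removal of the infected catheter". In-patient hospitalisation is an SAE criterion in 8.1.

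For a Class III device whose primary objective is safety and tolerability, infection is a central harm to watch. Section 10.4 expects the sponsor to act on unacceptable risk, and for that it needs the individual serious reports. Onward reporting under 8.3.2 depends on an event being classed as reportable, so an omission at the first step can carry through to the regulator and manufacturer.

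**Working it through.** **Does peritonitis fall under the exemption?**

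1. Section 8.2 refers to a section 7.7, but section 7 ends at 7.5. Trial Assessments is section 6.4.
2. Section 6.4 introduces "Additional visits for foreseeable adverse events related to treatment with a PD catheter" and refers the reader to Figures 2 to 4.
3. The caption of Figure 2 begins "Flow diagram of additional study procedures for PD peritonitis". The figure itself is not shown in the text at hand.
4. In 8.2 the sentence directly after the exemption is about peritonitis.

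Peritonitis is therefore covered by fair inference, although no valid list is cited.

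**Does an admitted episode fall under 8.3 as well?**

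1. The adverse event definition in 8.1 includes anticipated events, so foreseeability does not take an event out of AE or SAE status.
2. In-patient hospitalisation makes it an SAE under 8.1.
3. Section 8.3 covers every SAE whatever its relatedness. Expectedness (8.3.1.3) is a separate judgement, made only for device-related events, and does not decide whether an SAE is reported.

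**Do the triggers kept in 8.2 close the gap?** Only in part. An admitted peritonitis caused by a susceptible organism, or with a negative culture, that is not judged a catheter reaction and involves no migration meets none of the three. The 0.37 trigger concerns the aggregate rate and goes to the trial management committee, so it does not replace an individual report to the sponsor.

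**How often might this arise?** Inputs: 40 participants for 6 months (10.1) and 0.37 episodes per patient-year (8.2).

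- Exposure: 40 × 6 = 240 patient-months, which reproduces the figure in 10.1. 240 / 12 = 20 patient-years.
- Expected peritonitis episodes: 0.37 × 20 = 7.4.
- Share admitted: not given. Assumed 10% to 70%.
- Expected admitted episodes: 7.4 × 0.10 = 0.74 to 7.4 × 0.70 = 5.18.
- Chance of at least one (Poisson): 1 − exp(−0.74) = 52% to 1 − exp(−5.18) = 99%.
- Shorter exposure: 6.5 withdraws participants at catheter removal. At an assumed 15 patient-years, 0.37 × 15 = 5.55 episodes, of which 5.55 × 0.10 = 0.6 to 5.55 × 0.70 = 3.9 would be admitted.

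These figures count episodes to which both rules would apply. They do not count missed reports.

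**The case against.** The strongest reply is that 8.3 is categorical. A site that reads its rule on SAEs as governing will report every serious episode, and 8.2 then works as a waiver for routine, non-serious infections. That may well be what was meant. However, 8.2 does not say so, its heading covers serious events too, and no order of precedence is given. The objection limits the consequence to sites that follow 8.2; it does not remove the conflict.

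There are also other safeguards. The three retained triggers still send some infections and admissions to the sponsor, safety is reviewed at management group meetings, and the sponsor carries out monitoring and source data verification. These reduce the risk, but none of them is a 3-day report of an individual SAE.

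A reader might infer more than the protocol supports:

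- **That these episodes would be lost to the CRF and the primary analysis.** Section 8.2 names the medical records but does not say only there. Section 8.3 requires all AEs in the CRF, 6.4 requires the results and outcome of each PD infection to be recorded, Appendix 1 schedules AE assessment at visits from visit 3 on and at additional visits, and 10.3.3 analyses infection rates. The wording of 8.2 is untidy, but capture is already required.
- **That only the sponsor can stop the study.** Section 10.4 gives the sponsor that power without making it exclusive, and 6.5 allows early stopping for safety without naming who decides.
- **That catheter removal is itself a serious event caught by the exemption.** Under 8.1 an intervention counts only if it prevents life-threatening illness or permanent impairment. The Figure 4 caption concerns catheters no longer required.
- **That a stated number of SAEs, or most of the catheter-related ones, would go unreported.** The protocol gives neither the admitted share nor a total of such SAEs.

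**Conclusion.** The contradiction stands on the protocol's own text. For peritonitis with in-patient admission, 8.2 waives the sponsor report and 8.3 requires it within 3 calendar days. If staff follow 8.2, such an episode could fail to reach the sponsor and, through 8.3.2, the regulator and manufacturer, unless a retained trigger applies.

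The conflict is more likely than not to come up at full exposure: about 7.4 peritonitis episodes, of which roughly 0.7 to 5.2 would be admitted. This rests on the local rate applying, on the full 20 patient-years, and on an assumed admitted share of 10% to 70%. That peritonitis is within the exemption is inferred from 6.4, the Figure 2 caption and the adjoining text of 8.2. The finding concerns expedited safety reporting. It does not show that the adverse event analysis is undercounted.

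**What to change.** Reconcile the two sections in 8.2:

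1. State that the foreseeable-event exemption applies only to events that do not meet the SAE definition in 8.1, and that foreseeable events meeting it are reported under 8.3.
2. Replace the reference to section 7.7 with 6.4, so that staff can find which events are meant.
3. State that entry in the medical records is in addition to the CRF entry that 8.3 already requires.

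The cost is a few sentences of amendment and a few extra SAE forms. The design, sample size and analysis do not change.
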